Title: Comparison of Lesion Sterilization and Tissue Repair
Technique With Conventional Pulpectomy in the Treatment of
Pulpal Lesions in Primary Molars in Children

Unique Protocol ID : B.30.2.ATA.0.01.00/477

NCT Number : NCT07026435

Date : May 28, 2026

Document Type: Study Protocol and Statistical Analysis Plan

Study Protocol and Statistical Analysis Plan

This study will be carried out in the Department of Pediatric Dentistry of Atatürk University and pediatric patients between the ages of 4-10 who need endodontic treatment in primary molars I and II will be included in the study.

Inclusion Criteria

A. The criteria for inclusion in the study group are as follows:

1. Clinically and radiographically diagnosed with a pulpal lesion,
2. Inability to perform traditional pulpectomy treatment due to pathological or physiological root resorption exceeding 2/3 rate,
3. Not having a systemic disease,
4. No history of allergies (against antibiotics),
5. The patient and their parents agree to come to routine dentist check-ups and participate in the study, and
6. It is the refusal of the child and/or family to accept tooth extraction.

B. The criteria for inclusion in the study in the control group are as follows:

1. Clinically and radiographically diagnosed with a pulpal lesion,
2. Teeth that do not have pathological resorption and have physiological root resorption not exceeding 2/3 or have a traditional pulpectomy indication without physiological resorption,
3. Not having a systemic disease and
4. It is the agreement of the patient and their parents to come to routine dentist check-ups and participate in the study.

Exclusion Criteria

A. The study exclusion criteria in the study group are:

1. Those with systemic diseases,
2. Those who do not give the necessary consent for participation in the study, and
3. They are those who are allergic to antibiotics or other drugs.

B. In the control group, the study exclusion criteria were:

1. Those with systemic diseases,
 2. Those who do not give the necessary consent for participation in the study, and
- They are those who are allergic to antibiotics or other drugs.

Ethics Committee Approval

For our study, ethics committee approval was obtained with the letter "Atatürk University Faculty of Medicine Clinical Research Ethics Committee 12.07.2024 / Meeting number B.30.2.ATA.0.01.00 / Decision No: 477".

Sample Size:

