LSTR Group (Study Group): After local anesthesia is provided, rubber dam insulation will be made. The entrance cavity will be prepared using the #4 round bur and the necrotic tissue will be removed. Then, irrigation with saline and sodium hypochlorite will be performed. A cavity will be prepared for antibiotic paste with a depth of 2mm and a width of 1mm with a #4 tungsten carbide round bur at the channel mouths. If there is bleeding, a cotton pellet moistened with 5% sodium hypochlorite, which is an effective hemostatic agent, will be kept in the pulp chamber to stop the bleeding. 35% phosphoric acid was applied for 15 seconds to remove the smear layer, then the cavity will be washed and dried with saline. Since ciprofloxacin 500 mg antibiotic tablets are enteric-coated, their enteric coating will be completely scraped off with a scalpel and then pulverized in a clean mortar and stored in a moisture-free environment in glass bottles that do not receive light. The powder form of metronidazole is available on the market. In order to gain radioopacity of the powder (metronidazole and ciprofloxacin) prepared from a mixture of two antibiotics, it will be mixed with primary tooth canal filling material (Calcium Hydroxide Paste with Iodofome) (Viopex-Spident-Korea) to give a paste consistency. Antibiotic powders will be available in individual containers and the powders will be mixed with Viopex in the determined proportions (1:1) just before the application and the paste will be prepared freshly. Then, after the cavity is dried, the prepared pulp is placed in its cavity and covered with a light-curing, ready-to-use glass ionomer composite base cement (Ionoseal-VOCO-Germany) and the thread will be

restored with a stainless steel crown (Icrown-Seil Global-Korea) or composite filling (Twinky star-VOCO-Germany) (Picture 1). The upper restoration will be determined according to the child's adaptation status. (Stainless steel crown will be performed in children treated under general anesthesia, and composite restoration will be performed in children treated in routine dental clinics.) In case of swelling and lymphadenopathy in the tooth, additional systemic antibiotics will also be prescribed.

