Pulpectomy Group (Control Group): Traditional pulpectomy treatment will be applied. Local anesthesia will be applied to the lesion area and the cavity will be opened. The pulp tissue will be removed and after the canals are cleaned and irrigated, the primary tooth will be filled with canal paste (Calcium Hydroxide Paste with Iodofome) (Viopex-Spident-Korea). After the pulp chamber is sealed with a light-curing, ready-to-use glass ionomer composite base cement (Ionoseal-VOCO-Germany), the upper restoration will be done with a stainless steel crown (Icrown-Seil Global-Korea) or compound filling (Twinky star-VOCO-Germany) (Figure 2).

Clinical evaluations of the teeth in both the study and control groups will be performed at 3 months, 6 months and 1 year, and radiographic evaluations will be made at 6 and 12 months. These evaluations are necessary to monitor the effectiveness and course of treatment.

Evaluation Criteria in Follow ups

The effectiveness of the treatment will be evaluated on the following criteria:

- √ Relief of clinical symptoms (pain, swelling, etc.).
- √ Radiographically the state of healing of the lesion.
- √ In post-treatment follow-ups (3rd month, 6th month). Month and 12 Months) the status of lesion sterilization and tissue repair.

- √ Cessation of existing pathological root resorption (internal or external)
- √ Continuation of physiological root resorption in accordance with the age of the child.

Statistical & Analytical Methods:

The data obtained from our study will be entered into the Microsoft Excel program. Afterwards, necessary analyzes will be made with the IBM SPSS 20 statistical analysis program. Survival analyzes of the teeth participating in the study will be made according to months.

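### No masked or independent assessor and no scoring order is specified, although the clinical criterion is judgement-based, a film very probably reveals the arm, and clinical scoring could be partly masked at low cost

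*Combined protocol and SAP*

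**What the plan says.** The follow-up schedule, at the end of the Pulpectomy Group (Control Group) section, states that "Clinical evaluations of the teeth in both the study and control groups will be performed at 3 months, 6 months and 1 year" and that "radiographic evaluations will be made at 6 and 12 months". No film is scheduled at 3 months.

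Evaluation Criteria in Follow ups lists five criteria. The first is "Relief of clinical symptoms (pain, swelling, etc", with the list left open and no scale or threshold. The second, lesion healing, is expressly radiographic. The third, sterilization and repair at each follow-up, names no method of assessment. The last two concern pathological and physiological root resorption.

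The two techniques leave different material in the tooth:

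- LSTR Group (Study Group): "A cavity will be prepared for antibiotic paste with a depth of 2mm and a width of 1mm", at the canal mouths. The antibiotic powder is mixed with the canal filling material "In order to gain radioopacity of the powder (metronidazole and ciprofloxacin) prepared from a mixture of two antibiotics".
- Pulpectomy Group (Control Group): "after the canals are cleaned and irrigated, the primary tooth will be filled with canal paste", using the same radiopaque filling material.

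Root resorption decides the arm. Inclusion Criteria A requires "Inability to perform traditional pulpectomy treatment due to pathological or physiological root resorption exceeding 2/3 rate". Inclusion Criteria B requires no pathological resorption, and physiological resorption that is absent or not above 2/3.

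The coronal restorations are the same: one crown product or one filling product over one base cement. Treatment Protocol plans 28 crowns and 27 fillings in each arm.

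The document mentions no blinding, independent examiner, film reader, examiner calibration or order of scoring.

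**The concern.** The comparison is open and not randomised, and its clinical criterion depends on judgement. As written, the dentist who placed the paste may score the outcome, and may do so with the film in view. An assessor who expects one technique to do better can then move borderline teeth between success and failure differently by arm. A difference, or an apparent equivalence, could come partly from scoring.

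The only analysis named under Statistical & Analytical Methods is survival by month. Its event is not defined. If the event is treatment failure, each unmasked failure call enters the result directly.

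Masking is hardly possible for the radiographic criteria but partly possible for the clinical one, and the plan does not use that opportunity. It cannot be recovered once the visits have taken place.

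**Working it through.** The plan gives no figure for assessment bias, so there is none to reproduce on this point. Its sample-size output is not in dispute: with w = 0.4423761 and 6 degrees of freedom, λ = 70 × 0.4423761² = 13.699 and power is 0.8025, as stated under Sample Size.

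**Step 1. What would reveal the arm?**

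| Source of knowledge | LSTR | Pulpectomy | Reveals the arm? |
|---|---|---|---|
| Paste on film | Cavity 2 mm deep, 1 mm wide, at the canal mouths | Filled canals | Very probably |
| Root length on film | Resorption above 2/3 | Not above 2/3, none pathological | Very probably |
| Visible restoration | Same crown or filling products, 28/27 | Same crown or filling products, 28/27 | No |
| Treatment record, operator's memory | Known | Known | Yes |

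The first two rows are inferences from the described techniques and entry rules; the document does not say that films identify the arm. The third row is why masking the clinical examination is worth attempting.

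**Step 2. Which visits are exposed?**

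- 3 months: operator's knowledge, the treatment record and earlier films. No new film is scheduled.
- 6 and 12 months: the same, plus the film due at that time point.

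**Step 3. Scale, under assumptions.** Inputs: 55 teeth per arm (Treatment Protocol). The number of shifted teeth and the success rates are assumptions; the document gives neither.

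- Shift of 3 teeth: 3/55 = 5.5 points. Shift of 5 teeth: 5/55 = 9.1 points.
- Standard error of the difference: SE = √(2p(1−p)/55).

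| Assumed success p | SE | 3 teeth | 5 teeth |
|---|---|---|---|
| 80% | √(0.32/55) = 0.076 | 0.7 SE | 1.2 SE |
| 85% | √(0.255/55) = 0.068 | 0.8 SE | 1.3 SE |
| 90% | √(0.18/55) = 0.057 | 1.0 SE | 1.6 SE |

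**Step 4. Effect on a test.** Suppose there is no true difference and unmasked scoring lowers recorded success in one arm by b. The table gives the chance of a significant result in the favoured direction (two-sided 0.05, normal approximation; nominal 2.5%). The 38 per arm corresponds to about 30% loss: 55 × 0.7 = 38.5.

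| True success | Teeth per arm | b = 5 points | b = 10 points | b = 15 points |
|---|---|---|---|---|
| 80% | 55 | 9% | 23% | 42% |
| 80% | 38 | 8% | 17% | 31% |
| 90% | 55 | 12% | 31% | 55% |
| 90% | 38 | 10% | 23% | 40% |

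These tables show how sensitive the comparison is to a scoring shift. They do not estimate the shift in this trial.

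**The case against.** The strongest reply is that masking would achieve less here than it appears to.

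- **Pain is reported by the family.** Nothing masks them, and LSTR families entered only after refusing extraction. Masking the examiner does not mask that report. This stands.
- **The restoration hides the filling, not the tooth.** Advanced resorption may show at examination (mobility, for example, which is an assumption). This stands, and is why masking can only be partial.
- **Reach is limited.** Only one of the five criteria is plainly clinical; healing and root resorption are radiographic in substance. This stands.
- **Relief is a change from baseline.** A scorer shut out of the whole record could not judge it. This stands, and the fix provides for it.
- **Staffing is unknown.** The document does not say how many clinicians treat or examine, so a scorer who did not treat the tooth may not exist. This stands; the fix treats that step as conditional.
- **Confounding may matter more.** Resorption defines the arms, so case mix could produce a difference even with perfect masking. This is true, but assessment bias is a separate error that adds to it.

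A reader might also infer that masking is free, that it would give outcomes clear of this bias at every visit, that clinical and radiographic assessments share one visit, or that the plan gives clinical and radiographic criteria equal weight. The document supports none of these. Scheduling effort is needed; the family reports above remain unmasked; only shared time points are given, so a shared visit is an inference; and no composite or weighting is stated.

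None of this supplies the missing assessor or scoring order.

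**Conclusion.** The concern holds in a limited form. The plan specifies no masked or independent assessor and no order between clinical and radiographic scoring. Its clinical criterion is judgement-based, and a film very probably identifies the arm. Because the visible restorations match, clinical scoring can be partly masked at low cost, and the plan should do so.

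The illustrative scale is a shift of 5.5 to 9.1 points, or 0.8 to 1.3 standard errors at 85% success and 55 teeth per arm. It rests on an assumed 3 to 5 shifted teeth and an assumed success rate. A reader might take it as the bias present in the trial, or as the bias that the fix would remove. It is neither: the document does not permit an estimate, and any part arising from radiographic scoring would remain after the fix.

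The change reduces assessment bias without eliminating it and leaves confounding by resorption as it is. It should be made, but the trial does not stand or fall on it.

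**What to change.** Add to the follow-up schedule and Evaluation Criteria in Follow ups:

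1. At 3, 6 and 12 months, the clinical criteria are scored and signed before that day's film (6 and 12 months), earlier films and the treatment record are opened. The scorer works from a separate baseline-symptom sheet that does not show the arm, so that relief can be judged.
2. Where an existing study clinician who did not treat the tooth is available, that clinician scores. Otherwise the clinical result is reported as unmasked.
3. Clinical success is reported separately from radiographic success, and the radiographic result is labelled as assessed with knowledge of arm.
4. The report states what remains unmasked: family-reported pain, and possible clinical signs of advanced resorption.

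The cost is protocol wording, a fixed order of steps, one extra form and minor scheduling effort. No new staff, visits or procedures are needed. The price in interpretation is that the radiographic claim must be described as unmasked.

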It is planned to investigate the relationships between measurements in the main hypotheses of the research. Similar studies that can be used in the calculation of sample size were examined and the sample size calculation, which gives the highest number according to the statistical methods to be applied in line with the main hypotheses, was taken into account. In this study, using the program "G. Power-3.1.9.2" (Faul, F., Erdfelder et al. (2009)), at the 95% confidence level ($\alpha=0.05$), the standardized effect size was 0.4423 (Doneria, D., et al. (2017), Table 3; 6th month) (s.d.: 6) and the minimum sample size was obtained as 70 with a theoretical power of 0.80.

30% of the sample size (21 observations) was added to the study, which was calculated by taking into account the probability of observation loss over time. The minimum sample size for each time was calculated as 91. (Doneria et al., 2017; Faul et al., 2009)

The result of the analysis is as follows.

χ^2 tests - Goodness-of-fit tests: Contingency tables

Analysis: A priori: Compute required sample size

Input: Effect size w = 0.4423761

α err prob = 0.05

Power (1- β err prob) = 0.80

Df = 6

Output: Noncentrality parameter λ = 13.6987630

Critical χ^2 = 12.5915872

Total sample size = 70

Actual power = 0.8025413

Treatment Protocol

This controlled clinical trial included a comparison of the LSTR method with conventional pulpectomy in pulp lesions in primary molar teeth. The study involved 110 primary molar teeth and was divided into two groups: 55 with LSTR and 55 with conventional pulpectomy. In the LSTR group, 28 teeth will be covered with stainless steel crowns and 27 teeth will be restored with Compomer fillings. Likewise, in the traditional pulpectomy group, 28 teeth will be covered with a stainless steel crown and 27 teeth will be restored with a Compomer filling. Stainless steel crown and Compomer restoration teeth was determined according to the patient's compatibility status and the wishes of the parents/children.

Table

Working Group (LSTR)			Control Group (Pulpectomy)	
Restoration	Compomer	SSC	Compomer	SSC
Number of Teeth	27	28	27	28
Total	55		55	

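### Children are enrolled but teeth are counted and analysed, with no one-tooth-per-child rule and no allowance for within-child correlation; if any child contributes several correlated teeth, tooth-level standard errors and p values will be wrong.

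*Combined protocol and SAP*

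**What the plan says.** The opening paragraph defines the enrolled unit as the child: "pediatric patients between the ages of 4-10 who need endodontic treatment in primary molars I and II will be included". The Treatment Protocol section counts teeth: "The study involved 110 primary molar teeth and was divided into two groups: 55 with LSTR and 55 with conventional pulpectomy". The number of children appears nowhere. The inclusion and exclusion criteria for both groups set no limit on how many teeth a child may bring into the study.

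The Sample Size section uses a contingency-table chi-square with "Effect size w = 0.4423761", "α err prob = 0.05" and "Power (1- β err prob) = 0.80" on 6 degrees of freedom, giving "Total sample size = 70". It then allows for loss: "30% of the sample size (21 observations) was added to the study", which makes 91. No design effect or ICC enters the calculation.

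The Statistical & Analytical Methods section names Excel and SPSS 20 and then says: "Survival analyzes of the teeth participating in the study will be made according to months". It gives no survival method, variance estimator or child identifier.

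Group membership follows the state of root resorption of the tooth (item 2 of each inclusion list), so one child could have teeth in both groups.

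**The concern.** Teeth in one mouth share oral hygiene, caries activity and follow-up attendance, and some treatment choices in this plan depend on the child (restoration type follows the child's cooperation and the family's wishes). Outcomes of teeth in the same child are therefore plausibly correlated. The chi-square used for sizing, and survival methods in their ordinary form, treat every observation as independent.

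Two things are at stake. The first is the validity of standard errors and p values in the only analysis the plan describes. The second is power: correlated teeth carry less information than the same number of independent ones, and a child lost to follow-up takes all of its teeth out at once. If the dataset does not record which teeth belong to which child, neither problem can be corrected afterwards or seen by a reader.

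**Working it through.** **Inputs from the Sample Size and Treatment Protocol sections:** w = 0.4423761, α = 0.05, power 0.80, df = 6, minimum N = 70, loss allowance 30%, 110 teeth planned (55 per group).

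**Assumed, because the documents are silent:** m teeth per child from 1.25 to 3; ICC from 0.1 to 0.5; for the simulation, a 15% failure proportion.

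**1. The plan's own figure.** λ = N·w² = 70 × 0.4423761² = 13.6988. The critical χ² on 6 df is 12.5916. Power from the noncentral chi-square is 0.8025 at N = 70 and 0.7958 at N = 69. The stated 70 is reproduced exactly, as is 70 × 1.3 = 91. The calculation therefore uses a design effect of 1, that is, independent observations.

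**2. Type I error when a child's teeth are in the same group.** Design effect DE = 1 + (m − 1)·ICC. A naive two-sided 5% test on 1 df has true error 2·[1 − Φ(1.96/√DE)].

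| m | ICC | DE | Formula | Simulation |
|---|---|---|---|---|
| 2 | 0.2 | 1.20 | 7.4% | 7.2% |
| 2 | 0.3 | 1.30 | 8.6% | 8.7% |
| 2 | 0.5 | 1.50 | 11.0% | 11.2% |
| 3 | 0.3 | 1.60 | 12.1% | 11.9% |

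The simulation is beta-binomial, with 100,000 runs, 15% failure and 55 teeth per group. With independent teeth it returns 4.9%, so the excess comes from the clustering.

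If most children give one tooth (mean m = 1.25, ICC 0.1 to 0.5), DE is 1.025 to 1.125 and the formula gives 5.3% to 6.5%. This treats cluster sizes as equal; unequal sizes raise it a little.

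**3. Type I error when a child's teeth are in both groups.** If every child has one tooth in each group, the true variance of the difference is (1 − ICC) times the naive variance. At ICC 0.3: 1.96/√0.7 = 2.34, and 2·[1 − Φ(2.34)] ≈ 2%. The naive test is then conservative and loses power.

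**4. Power on the plan's own chi-square, using effective N = N/DE (same-group teeth).**

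| Teeth | DE 1.0 | DE 1.2 | DE 1.3 | DE 1.5 | DE 1.6 |
|---|---|---|---|---|---|
| 110 (no loss) | 0.957 | 0.91 | 0.88 | 0.82 | 0.79 |
| 77 (110 × 0.7) | 0.845 | 0.76 | 0.72 | 0.65 | 0.61 |

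The largest design effect that keeps 70 effective teeth is 110/70 = 1.57 with no loss and 77/70 = 1.10 with 30% loss.

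**The case against.** The strongest reply is that nothing in the documents says any child contributes more than one tooth. The reference to first and second primary molars can be read as naming eligible tooth types. If each child gives one tooth, the concern disappears. A reader might infer from the mention of general anaesthesia that several study molars are treated in one session. The text links anaesthesia only to the type of restoration and does not say this.

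Second, the plan does not state that teeth will be analysed as independent. It names no survival method at all. Independence is explicit only through the choice of test for the sample size; for the analysis it is inferred from silence.

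Third, the direction is open. A reader might conclude that false positives are inflated. That holds only for teeth in the same group; group follows each tooth's resorption, so the net sign cannot be determined from the documents.

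Fourth, 110 teeth exceed both 70 and 91. Before loss, power is still 0.88 at a design effect of 1.3 and 0.79 at 1.6, so the documents do not show that the trial is too small.

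Fifth, the type I error figures use a 1-df comparison of proportions, which is neither the 6-df chi-square nor a survival analysis.

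All five stand as limits on certainty, direction and size. They do not remove the gap: the plan permits several teeth per child, does not say how they would be handled, and describes only a tooth-level analysis. The surplus of teeth can offset some lost power but cannot correct a standard error.

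**Conclusion.** The point holds in conditional form. If any child contributes more than one tooth and outcomes within a child are correlated, a tooth-level analysis gives wrong standard errors and p values: too small for same-group teeth, too large for teeth split between groups. That they will be wrong in any event is a stronger reading, and the documents do not support it.

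The size is illustrative only. Across the assumed values, the true error of a nominal 5% test runs from about 2% (all children paired across groups, ICC 0.3), through little change (mostly one tooth per child), to about 11% or 12% (two same-group teeth at ICC 0.5, or three at ICC 0.3).

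With two teeth per child and ICC up to 0.5, the stated power of 0.80 is at risk only when clustering and loss combine: at 77 remaining teeth it is 0.76 at a design effect of 1.2 and 0.65 at 1.5. Without loss, the design effect would have to exceed 1.57. The omission is certain from the text; its direction and size are not.

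**What to change.** Record a child identifier for every tooth, and state one of two rules.

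- **One study tooth per child**, with the way that tooth is chosen fixed in advance. Ordinary tooth-level methods then raise no clustering problem, but 110 teeth would need 110 children.
- **The child is the cluster.** For example: *Tooth outcomes at the 3, 6 and 12 month visits will be compared between groups with a GEE model clustered on child, with robust standard errors. Any Cox or other survival model will use variance clustered on child.* This covers teeth in the same group and teeth split between groups. It needs a defined tooth-level outcome, and the team should confirm that SPSS 20 supports the chosen models, particularly the clustered survival model.

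Under either rule, report the number of children and the teeth per child by group. In the Sample Size section, state that 70 and 91 assume independent teeth, or restate power with an assumed design effect and its basis.

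The cost is a few sentences and one data column. If children contribute several same-group teeth, intervals widen: standard errors grow by about 14% at a design effect of 1.3 (√1.3 = 1.14) and 26% at 1.6 (√1.6 = 1.265). If each child contributes one tooth, results change essentially not at all.
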